### **9.7.3. Prohibited Concomitant Procedures**

Procedures prohibited prior to study entry are described in the exclusion criteria in Section [8.2](#).

Subjects should not receive a blood transfusion at the Day 1 or Week 4 visit. If a subject does require a blood transfusion at the Day 1 or Week 4 visit, the medical monitor should be notified for further guidance.

## **9.8. Handling and Disposal**

At the end of the study, a final reconciliation must be made between the quantity of study drug supplied, dispensed, and subsequently returned to the sponsor. A written explanation must be provided for any discrepancies. After accountability has been performed by the sponsor or sponsor's designee, any unused study drug remaining at the end of the study will be returned to the sponsor for destruction. Onsite destruction of unused study drug will be permitted with prior notice and approval from the sponsor.

## 10. RANDOMIZATION AND BLINDING

### 10.1. Randomization

All subjects who are screened (including screen failures) will be assigned a unique subject identification number.

On Day 1, eligible subjects in Population 1 (TDT) and Population 2 (NTDT) will be assigned another unique number (randomization number) in sequential order. The randomization number codes the subject's initial treatment assignment according to the randomization schedule generated prior to the study. Initially, subjects will be randomly assigned in a 2:1 ratio to receive either IMR-687 lower dose or placebo. If the DMC recommends inclusion of the higher dose, randomization will then proceed in a 1:2:1 ratio (IMR-687 lower dose, IMR-687 higher dose, or placebo).

Subject randomization will be stratified by TDT/NTDT status.

Randomization numbers will not be re-used once assigned. If a subject discontinues or is discontinued at the discretion of the investigator or DMC up to and including the Week 12 visit, the subject may be replaced with another subject meeting the eligibility criteria. In the event that a subject is replaced, the replacement subject will receive the same treatment as the replaced subject, and a different leading number will be used for the replacement randomization number.

### 10.2. Blinding

To ensure that the subject and site are blinded with respect to each subject's treatment assignment, placebo tablets and tablets for each dose level of IMR-687 are identical in appearance and are supplied in identical packaging. Each bottle will contain a code that identifies the contents as either 100 mg IMR-687, 150 mg IMR-687, 200 mg IMR-687, or placebo.

Every attempt should be made to preserve the integrity of study drug blinding. Except for cases of emergency unblinding, as described in Section 10.4, the randomization code will remain unbroken for subjects and study personnel at the site until the database has been locked for each study population. The blinded sponsor and CRO study team members will only be unblinded to the analysis results at the conclusion of the study (e.g., database lock).

### 10.3. Unblinding for Interim Analysis

To facilitate the analyses, certain sponsor representatives and designees will be unblinded to treatment assignments prior to and during the interim analysis (including the unblinded contract research organization [CRO] biostatistician and external groups for bioanalytical, PK, and PK/PD analyses and QoL analyses). Details will be provided in the study unblinding plan.

### 10.4. Emergency Unblinding

Unblinding is not always necessary to provide effective medical intervention and subject management in the event a subject experience an SAE, or an event that results in cessation of treatment (see Section 8.7). However, in the exceptional circumstance where the investigator believes that knowledge of the study drug assignment is essential to provide appropriate medical management, the treatment assignment for that subject will be provided to the investigator

according to standard operating procedures at the CRO. The medical monitor and sponsor are available to the investigator as needed for any considerations of unblinding a specific subject; however, the decision to unblind a specific subject relies solely on the clinical judgement of the investigator. That is, there is no requirement to discuss with the medical monitor and/or sponsor prior to unblinding a specific subject by the investigator; however, consultation is preferred. In the event that the investigator must unblind a subject and has not consulted with the medical monitor and/or sponsor, the investigator should notify the medical monitor and sponsor of the unblinding within 24 hours of breaking the blind.

After breaking the blind, the site staff should record the reason(s) for breaking the blind and any AEs leading to the breaking of the blind in the source documents and the appropriate eCRF pages. After breaking the blind, the subject will be discontinued from the study and should proceed with early termination and end of study visits as described in Section 8.4 and per the schedule of assessments ([Table 2](#) and [Table 3](#)).

## 11. ASSESSMENTS

[Table 2](#) and [Table 3](#) list all of the study assessments and procedures for Population 1 (TDT) and Population 2 (NTDT), respectively. All data obtained from these assessments must be documented in the subject's source documentation.

Subjects should be seen for all visits on the designated day or within the defined allowable visit window ([Table 2](#) and [Table 3](#)). The visits are as follows:

- Screening (up to 28 days prior to Baseline)
- Baseline (Day 1)
- Treatment Period (Week 1 to Week 36)
  - Telephone visit will be performed at Week 2
- End of Treatment/Early Termination (Week 36)
- End of Study (Week 40)

Unless otherwise specified, all assessments should be completed prior to dosing at any given timepoint.

### 11.1. Screening and Baseline Activities

The descriptions below are for screening-specific activities. For descriptions of activities that occur during both the screening and treatment periods, refer to Section [11.2](#) for preliminary efficacy and PD assessments, Section [11.3](#) for safety assessments, and Section [11.4](#) for PK assessments.

#### 11.1.1. Informed Consent

The subject must read, understand, and sign the IRB/IEC-approved ICF confirming his or her willingness to participate in this study before initiating any screening activity that is not standard of care. The investigator will ensure that the subject has received adequate language translation if needed and understands the ICF before signing as per the local IRB/IEC's requirement. Subjects must also grant permission or be informed of national laws for the processing and dissemination of their personal data, including data concerning health (sensitive/protected health information) and the use and retention of their specimens for study-related purposes.

Informed consent for an optional pharmacogenomics evaluation will be offered at screening.

#### 11.1.2. Demographic Information and Medical/Disease History

Subject demographics (age, sex, race, and ethnicity) and medical disease history (by thorough review of medical records and by interview) will be recorded at screening, in accordance with country requirements and institutional policies, and captured in the eCRF. Concurrent medical signs and symptoms must be documented to establish baseline severities.

Disease history should contain a confirmed diagnosis of  $\beta$ -thalassemia or HbE/ $\beta$ -thalassemia. Concomitant alpha gene deletion, duplication, or triplication is allowed.

### **11.1.3. Inclusion/Exclusion Criteria Evaluation**

Eligibility will be assessed at screening and baseline based on the inclusion and exclusion criteria provided in Section 8. All inclusion and exclusion criteria will be assessed at the Screening visit; continued eligibility based on these criteria will be confirmed on Day 1.

### **11.1.4. Eastern Cooperative Oncology Group Performance Score**

Subjects' performance status will be measured by ECOG at Screening ([Appendix 1](#)).

### **11.1.5. Historical Transfusion Burden**

After obtaining signed informed consent, the subject's transfusion history for the 12 weeks prior to Baseline (Day 1) visit date should be recorded, relying on the documentation examples detailed below. Note that any transfusion on Day 1 (i.e., after randomization) should not be included in the transfusion history.

In order to be eligible for the study, the dates of transfusion events and the number of pRBC units per event within the 12 weeks preceding the Baseline (Day 1) visit must be available. If available, the following data should also be collected for each transfusion event: volume and hematocrit of each pRBC unit, pre-transfusion Hb, and pre-transfusion weight.

**For TDT subjects:** In the case of a subject receiving a transfusion after signing the ICF, a transfusion on the day of the Baseline (Day 1) visit may occur only after all study assessments are completed, including all PK sampling.

**For NTDT subjects:** In the case of a subject receiving a transfusion after signing the ICF, but prior to randomization, the investigator would inform the medical monitor. The intent is to avoid transfusions within the 2-week period leading to randomization. Approval could be obtained for the screening period to be extended by a maximum of 14 days.

### **11.1.6. Height**

Height in centimeters (cm) will be measured at screening.

### **11.1.7. Serum Virology**

Blood samples will be collected for serum virology (screening assessment) only if clinically indicated. Testing will be performed through a central laboratory and may include hepatitis B surface antigen (HBsAg), hepatitis A immunoglobulin M (IgM), and hepatitis C virus (HCV) antibody, as well as HIV testing.

### **11.1.8. Pharmacogenomic Evaluation (Optional)**

Blood samples may be collected at screening if the subject provides informed consent. The pharmacogenomic evaluation will include alpha-globin, gamma-globin *XmnI* polymorphism, and BAF chromatin remodeling complex subunit 11A (BCL11A), among other potential markers. The results of pharmacogenomic analyses may be reported separately from the clinical study report. Pharmacogenomic samples will be stored for up to 5 years post-study completion.

## 11.2. Preliminary Efficacy and Pharmacodynamic Assessments

### 11.2.1. Transfusion Burden

Transfusion burden will be assessed according the schedule of assessments ([Table 2](#) and [Table 3](#)) using the following variables: dates of transfusion events, number of pRBC units per event, volume and hematocrit of each pRBC unit, pre-transfusion Hb, and pre-transfusion weight. These variables may also follow the same documentation requirements outlined in [Section 11.1.5](#).

If a subject requires a transfusion on days when PK samples will be drawn (i.e., the Baseline [Day 1] or the Week 1, Week 3 [TDT]/Week 4 [NTDT], Week 24, or Week 36 visits), the transfusion can only be performed after the final PK sampling.

### 11.2.2. Quality of Life

Quality of life will be assessed using the TranQOL and SF-36 QoL tools in the TDT population ([Table 2](#)) and the NTDT-PRO and SF-36 QoL tools in the NTDT population ([Table 3](#)).

The TranQoL ([Klaassen 2013](#); [Klaassen 2014](#)) is a disease-specific QoL measure for children and adults with thalassemia major. It has four versions: (i) a child self-report, (ii) an adult self-report, (iii) a parent self- report (measuring the impact of the disease on the parent), and (iv) a parent proxy report (measuring the child's QoL). The questionnaire length ranges from 29 items (child) to 39 items (parent). The questions are grouped into 4 domains: physical health, emotional health, family functioning, and school and career functioning. The adult and parent self-report questionnaires include a fifth category on sexual activity which is only one item. For this study only, the adult self-report will be used.

The SF-36 ([Hays 2004](#)) is a 36-item, patient-reported survey of patient health. The SF-36 consists of 8 scaled scores, which are the weighted sums of the questions in their section. Each scale is directly transformed into a 0 to 100 scale based on each scale having equal weight. The lower the score the more disability and the higher the score the less disability (i.e., a score of 0 is equivalent to maximum disability and a score of 100 is equivalent to no disability). The 8 sections are: vitality, physical functioning, bodily pain, general health perceptions, physical role functioning, emotional role functioning, social role functioning, and mental health.

The NTDT-PRO ([Taher 2019](#)) is a new disease-specific health-related QoL tool for patients with NTDT. The NTDT-PRO was designed as a daily diary with recall of thalassemia-related symptoms over the previous 24 hours. The relatively short recall period is used due to the high level of day-to-day variation in symptoms experienced by patients with NTDT.

The 6 NTDT-PRO items assess the presence or severity of specific symptoms using a numerical rating scale ranging from 0 (“absent/minimal”) to 10 (“extreme/high”): tiredness with or without physical activity, weakness with or without physical activity, and shortness of breath with or without physical activity. NTDT-PRO items are grouped into 2 domains: tiredness/weakness (tiredness with physical activity, tiredness without physical activity, weakness with physical activity, and weakness without physical activity) and shortness of breath (shortness of breath with physical activity, shortness of breath without physical activity). For this study, the

NTDT-PRO will not be used as a daily diary; data will be collected as per the schedule of assessments ([Table 3](#)).

### **11.2.3. Specialty Hematology**

Blood samples will be collected prior to study drug administration for HbF and percent F-cells at selected study visits as shown in the schedule of assessments ([Table 2](#) and [Table 3](#)). Refer to the specialty laboratory manual for details on the collection, handling, and processing of blood samples.

### **11.2.4. Pharmacodynamic Markers**

Blood samples will be collected prior to study drug administration for the following PD laboratory assessments at selected study visits as shown in the schedule of assessments ([Table 2](#) and [Table 3](#)).

Pharmacodynamic assessments will include the following:

- Haptoglobin
- Hepcidin-25
- Serum ferritin
- Soluble transferrin receptor
- Soluble E-selectin
- Soluble P-selectin
- Soluble intercellular adhesion molecule 1 (ICAM-1)
- Vascular cell adhesion molecule 1 (VCAM-1)
- High-sensitivity C-reactive protein (hsCRP)
- Serum N-terminal pro-B-type natriuretic peptide (serum NT-proBNP)
- Serum iron and total iron binding capacity (TIBC) for calculated transferrin saturation
- Erythropoietin

Refer to the central laboratory manual for details on the collection, handling, and processing of blood samples.

## **11.3. Safety Assessments**

### **11.3.1. Telephone Visits**

Qualified site personnel will contact the subject by telephone at Week 2 to capture potential TEAEs and concomitant medications. Subjects will also be reminded of compliance with study drug and the next visit schedule. If any AEs of significant clinical concern are identified during the telephonic visit, the subject will be requested to come into the site to be assessed.

### 11.3.2. Vital Signs

Vital signs include heart rate, respiratory rate, blood pressure, and body temperature. Vital signs should be consistently measured in either the sitting or semi-supine position. Vital signs will be collected at every visit except for the telephone visits. Vital signs will be taken pre-dose and 2 hours ( $\pm 20$  minutes) post-dose on Day 1 and Week 3 for TDT subjects and on Day 1 and Week 4 for NTDT subjects (during PK assessments). At all other timepoints, vital signs can be taken irrespective of taking study drug. Vital signs that are clinically significant and not explained by the underlying disease or concomitant medications should be recorded as AEs in the eCRF.

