### 5.2.2.3. Cardiovascular

In nonclinical safety pharmacology and 14-day GLP toxicology studies in beagle dogs, IMR-687 appeared to result in increases in heart rate that did not appear to be dose dependent. In the safety pharmacology study in dogs, at doses of 75 mg/kg, statistically significant changes in heart rates were observed. In the 14-day toxicology study in dogs, the highest heart rates were noted at the highest dose level of 75 mg/kg but did not reach statistical significance. In a subsequent 9-month study in dogs at doses up to and including 50 mg/kg/day, there was no evidence of any increases in heart rate and there were no histopathological abnormalities noted in cardiac tissue. In healthy volunteers in the first-in-human study, at doses between 0.3 to 6 mg/kg, sporadic observations of sinus tachycardia (i.e., heart rates >100 bpm) occurred in various subjects, including a subject in the MAD on placebo. The contribution of concomitant AEs such as headache to the rise in heart rate could not be excluded. No dose dependency or dose-duration dependency was noted for these heart rate observations. No signs of prolongation of corrected QT interval, Fridericia's formula (QTcF) were noted in any cohort of healthy volunteers at any dose of IMR-687. In the interim safety analysis of Study IMR-SCD-102, with respect to vital signs, there were no observable changes in systolic, diastolic blood pressure and pulse, and there were no changes in respiratory rate. In the IMR-SCD-102 clinical study, the mean interim steady state AUC0-24 was 16,300 ng•hr/mL for the 200 mg (~2.9 mg/kg) IMR-687 dose level. In the 39-week dog toxicology study mentioned above, mean AUC0-24 was ≥87,500 ng•hr/mL at the NOAEL in female dogs, resulting in safety margins of at least ~5.3-fold for the 200 mg clinical dose.

Monitoring of vital signs is recommended for subjects in IMR-687 studies. In the event of noted persistent and/or clinically significant tachycardia, other causes of tachycardia, particularly pain and dehydration, should also be considered.

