**Table 1: Study Endpoints**

Primary Endpoint	TDT	NTDT
IMR-687 safety and tolerability as measured by: 
 
• Incidence and severity of adverse events and serious adverse events
 
• Observed values and changes from baseline in 12-lead ECG parameters, clinical laboratory tests (chemistry, hematology, coagulation, urinalysis), and vital signs for any timepoint
 
• Physical examination findings
 
• Use of concomitant medications and therapies
 
	X	X
Secondary Endpoints	TDT	NTDT
Proportion of subjects with a $\geq 20\%$ hematological improvement (as measured by reduced transfusion burden) a from Week 12 to Week 24 and Week 24 to Week 36, compared to the 12 weeks prior to Baseline (Day 1).	X	
Proportion of subjects with a $\geq 20\%$ hematological improvement (as measured by reduced transfusion burden) a from Week 12 to Week 36, compared to the 12 weeks prior to Baseline (Day 1).	X	
Proportion of subjects with a $\geq 33\%$ hematological improvement (as measured by reduced transfusion burden) a from Week 12 to Week 24 and Week 24 to Week 36, compared to the 12 weeks prior to Baseline (Day 1).	X	
Proportion of subjects with a $\geq 33\%$ hematological improvement (as measured by reduced transfusion burden) a from Week 12 to Week 36, compared to the 12 weeks prior to Baseline (Day 1).	X	
Mean number of transfusion events from baseline to Week 36.	X	

Secondary Endpoints (continued)	TDT	NTDT
The plasma PK profile of IMR-687 (and metabolites) after administration to subjects will be evaluated by determination of PK parameters (e.g., $C_{max}$ , $t_{max}$ , $t_{1/2}$ , and $AUC_{0-24}$ ) and population PK, based on drug concentration levels in plasma obtained over time.	X	X
Mean change from baseline to Week 36 for iron chelation therapy daily dose and serum ferritin.	X	X
Proportion of subjects with an increase from baseline of $\geq 1.0$ g/dL in mean Hb values at Weeks 12 to 24 and Weeks 24 to 36 in the absence of transfusions.		X
Mean change from baseline in mean Hb values at Weeks 12 to 24 and Weeks 24 to 36 in the absence of transfusions.		X
Mean change from baseline in mean HbF values at Weeks 12 to 24 and Weeks 24 to 36 in the absence of transfusions.		X
Proportion of subjects with an increase from baseline of $\geq 3\%$ in mean HbF values at Weeks 12 to 24 and Weeks 24 to 36 in the absence of transfusions.		X
Exploratory Endpoints	TDT	NTDT

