### 11.3.5. Electrocardiogram

TriPLICATE 12-lead ECGs will be performed to evaluate the change from baseline in ECG parameters (heart rate, PR interval, RR interval, QRS duration, QT interval, and QTcF interval). For TDT subjects, ECGs will be obtained at pre-dose and 2 hours ( $\pm 30$  minutes) post-dose at Baseline and at Week 3. For NTDT subjects, ECGs will be obtained at pre-dose and 2 hours ( $\pm 30$  minutes) post-dose at Baseline and at Week 4. At all other timepoints, ECGs will be taken pre-dose.

Interpretation of ECG tracings must be made by a qualified physician and documented on the ECG eCRF(s). The instrument used in the study to assess the ECG should be calibrated per the institution's standard policy.

Clinically significant abnormalities present prior to the subject's signed informed consent should be reported on the medical history eCRF. New or worsened clinically significant findings occurring after informed consent must be recorded on the AE eCRF as described in Section [12.1.2.3](#).

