## 12. SAFETY MONITORING AND REPORTING

### 12.1.1. Adverse Event and Serious Adverse Event Collection

#### 12.1.1.1. Time Period Adverse Event Collection

All AEs and SAEs, related and unrelated, will be recorded from the signing of informed consent through the end of study safety follow-up visit (Week 40). Events that occur following administration of study drug will be considered TEAEs.

All SAEs will be recorded and reported to the sponsor or sponsor's designee within 24 hours, as indicated in Section 12.1.2.3. The investigator will also submit any updated SAE data to the sponsor within 24 hours of the data being available.

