### 12.1.2. Adverse Event Recording and Reporting

#### 12.1.2.1. Definitions

##### 12.1.2.1.1. Definition of an Adverse Event

An AE is defined as any untoward medical occurrence in a clinical study subject administered a pharmaceutical product and which does not necessarily have to have a causal relationship with this treatment. An AE can therefore be any unfavorable or unintended sign (for example, an abnormal laboratory finding), symptom, or disease temporally associated with the use of a medicinal (investigational) product, whether or not considered related to the medicinal (investigational) product.

Examples of AEs include but are not limited to:

- Abnormal test findings
- Clinically significant symptoms and signs
- Changes in physical examination findings
- Hypersensitivity
- Drug abuse
- Drug dependency

Additionally, they may include the signs or symptoms resulting from:

- Drug overdose
- Drug withdrawal
- Drug misuse

- Drug interactions
- Extravasation
- Exposure during pregnancy
- Exposure via breastfeeding
- Medication error

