#### Possible:

- Event or laboratory test abnormality, with reasonable time relationship to drug intake
- Could also be explained by disease or other drugs
- Information on drug withdrawal may be lacking or unclear

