13.6.2.1 Adverse Events

MedDRA Coding

AEs will be coded using MedDRA (v23.0 or higher).

Treatment-emergent adverse event (TEAE)

A treatment-emergent adverse event (TEAE) is defined as an AE that emerges on or after the initiation of study drug, or an AE that existed pre-treatment and worsened in severity on or after the initiation of study drug, through 30 days after the last dose of study drug. A pre-treatment adverse event is an AE that emerges before the date of initiation of study drug.

Refer to Appendix 3 for handling of partial dates for AEs for the purpose of assigning treatment-emergent flags. In the case where it is not possible to define an AE as treatment emergent or not, the AE will be classified as treatment emergent.

Severity

Severity is classified as Grade 1: Mild, Grade 2: Moderate, Grade 3: Severe, Grade 4: Life Threatening, Grade 5: Death Related to AE, using the Common Terminology Criteria for Adverse Events, v5.0 (CTCAE v5.0). For the AE summary by CTCAE severity grade, an AE with missing CTCAE severity grade will not be imputed. Imputed values will not be included in data listings.

Relationship to Study Treatment

Relationship is classified as “Unlikely/Not related”, “Possible”, “Probably/Likely”, or “Certain/Related” by the Investigator. A “treatment-related TEAE” for the purpose of this summary is defined as a TEAE with relationship to study drug of “Possible”, “Probably/Likely” or “Certain/Related”. For the AE summary by relationship, an AE with a missing relationship to study drug will not be imputed. Imputed values will not be included in data listings.

TEAEs Leading to Discontinuation of Study Treatment

TEAEs leading to discontinuation of study treatment will be identified by action taken with study treatment being recorded as “Drug withdrawn” on the Adverse events CRF.

Serious and Non-Serious TEAEs

Serious adverse events (SAEs) are those events recorded as “Yes” for the question “Was the adverse event serious?” on the Adverse Event CRF.

TEAEs Leading to Death

TEAEs leading to death are those events which are recorded as “Yes” for the question “Did the adverse event result in death?”, or recorded CTCAE Toxicity Grade 5, or with outcome = “Fatal” on the Adverse Events CRF.

TEAEs Leading to Study Discontinuation

TEAEs leading to study discontinuation are those events which are recorded as “Yes” for the question “Did the adverse event cause the subject to be discontinued from the study?” on the Adverse events CRF.

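### Protocol 11.3.2 puts a cause test on recording vital-sign AEs that Section 12 does not allow, so sites following it can under-record part of the primary AE endpoint

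*Protocol*

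**What the plan says.** Protocol 11.3.2 (Vital Signs): "Vital signs that are clinically significant and not explained by the underlying disease or concomitant medications should be recorded as AEs in the eCRF". This sets two conditions, clinical significance and the lack of an explanation by disease or concomitant medication.

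Protocol Section 12 sets no condition on cause:

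- 12.1.2.1.1 defines an AE as an occurrence that "does not necessarily have to have a causal relationship with this treatment".
- 12.1.1.1: "All AEs and SAEs, related and unrelated, will be recorded from the signing of informed consent".
- 12.1.2.3 requires every AE, serious or not, to go into the eCRF.
- 12.1.2.2.2 has the investigator grade causality for every AE. One feature of the grade Possible is "Could also be explained by disease or other drugs". The grade Unlikely/Not Related covers events for which disease or other drugs offer a plausible explanation.

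Protocol 11.3.5 (Electrocardiogram): "New or worsened clinically significant findings occurring after informed consent must be recorded on the AE eCRF". Section 11.3.6 likewise sends each clinically significant laboratory result after screening to the AE form. Neither mentions cause.

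The first component of the primary endpoint in Protocol Table 1 is "Incidence and severity of adverse events and serious adverse events". In SAP 13.6.2.1 a treatment-related TEAE "is defined as a TEAE with relationship to study drug of" Possible, Probably/Likely or Certain/Related.

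**The concern.** The same event meets two instructions. Section 12 says to record it and then judge its cause. Section 11.3.2 reads as if the cause is judged first and recording follows only when no other explanation is found. An event left off the AE form gets no CTCAE grade, causality grade or action taken, and it does not appear in any TEAE table.

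Increased heart rate is discussed among the potential risks in Protocol 5.2.2.3. That section tells investigators who see persistent or clinically significant tachycardia that "other causes of tachycardia, particularly pain and dehydration, should also be considered". This is sensible when assessing a patient. Combined with 11.3.2, though, it could prompt a site to settle on another explanation before deciding whether to record the event. With approximately 50 sites planned, some may follow 11.3.2 and others Section 12, and AE capture would then differ by site.

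**Working it through.** The documents state no figure on this point, and none can be derived. The check is a comparison of the rules.

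**1. Recording rules by type of finding**

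| Finding | Section | Clinical significance required? | Cause condition? |
|---|---|---|---|
| Vital signs | Protocol 11.3.2 | Yes | Yes: not explained by disease or other drugs |
| Physical examination | Protocol 11.3.4 | Yes; new or worse, and meeting the AE definition | No |
| ECG | Protocol 11.3.5 | Yes; new or worse | No |
| Laboratory | Protocol 11.3.6 | Yes | No |
| All AEs | Protocol 12.1.1.1, 12.1.2.1.1, 12.1.2.3 | Not stated | No; related and unrelated alike |

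Clinical significance is a common filter. The cause condition appears only for vital signs.

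**2. What the causality scale would do with the filtered events.** Take a clinically significant vital-sign change with a reasonable time relation to dosing, for which disease or another drug is a candidate cause. If recorded, it fits Possible when the alternative is only a candidate, and Unlikely/Not Related when the alternative is plausible and the timing makes a drug effect improbable. Either way it is an AE. Under 11.3.2, once the investigator regards it as explained, it need not reach the scale at all. An event that would have been graded Possible is then missing from both the TEAE and the treatment-related TEAE counts. One that would have been graded Unlikely/Not Related is missing from the TEAE counts only.

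**3. Which heart-rate findings have another route.** Heart rate is also an ECG parameter (Protocol 11.3.5), so a clinically significant change seen on ECG goes to the AE form whatever its cause.

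- NTDT (Protocol Table 3): vital signs and ECG are both scheduled at every on-site visit.
- TDT (Protocol Table 2): vital signs are scheduled at 14 on-site visits after baseline (Weeks 1, 3, 6, 9, 12, 15, 18, 21, 24, 27, 30, 33, 36, 40). ECG is absent at Weeks 9, 15, 21, 27 and 33, so it is present at 14 − 5 = 9.

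Blood pressure, respiratory rate and temperature have no such second route.

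**4. What the SAP recovers without the AE form.** SAP 9.0 and 13.6.2 make clinically significant vital-sign change a separate part of the primary endpoint. SAP 13.6.2.3 summarises all vital signs by visit. Its Table 6 counts threshold crossings for heart rate, systolic and diastolic pressure, including unscheduled visits, regardless of cause. Table 6 has no threshold for respiratory rate or temperature, and none of these outputs carries AE severity, relatedness or action taken.

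**The case against.** Section 11.3.2 says what should be recorded and does not forbid recording anything else. Section 11.3.7 refers AE collection to Section 12, where the rule is mandatory, so a careful site would record these events anyway. That stands, and it makes this a contradiction between two instructions rather than an outright exclusion. It does not remove the problem, because a site reading the vital-signs section alone is given the narrower rule.

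A finding judged to be explained is arguably closer to Unlikely/Not Related than to Possible, because the latter describes remaining uncertainty. This also stands in part. Some overlap with Possible is plausible, but the text does not show a material loss from the treatment-related table.

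A reader might infer that the trial's heart-rate signal is hidden. The documents do not support that. The ECG route and the vital-sign summaries remain, SAP 13.6.2.3 adds a heart-rate shift plot, and the DMC may review vital signs directly (Protocol 7.2). Protocol 5.2.2.3 also reports no dose dependency in healthy volunteers, no heart-rate increase in the 9-month dog study and no observable pulse change in the interim analysis of the sickle cell study.

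A reader might also infer that, because these subjects are anaemic, a disease explanation for a fast heart rate can almost always be found. The documents do not say how often one would be invoked.

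Nor are discontinuations lost altogether. Protocol 8.5.1 requires their circumstances to be recorded, and SAP 13.1 tabulates the primary reason.

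**Conclusion.** The contradiction is established from the text. Sites that follow 11.3.2 can leave out vital-sign AEs that Section 12 requires, so the AE component of the primary endpoint can be under-recorded or captured inconsistently across sites.

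The size cannot be stated. It would need the rate of clinically significant vital-sign findings, the share investigators attribute to disease or other drugs, and the share of sites following the narrower rule. The documents give none of these. Applying assumed shares to assumed event rates would say nothing about this trial.

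A bias for or against IMR-687 cannot be claimed either. The judgement is made under blinding, and nothing shows whether the attributed share would differ between arms.

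The conclusion assumes only that some sites will read 11.3.2 as the operative rule for vital signs. The loss is partial, since the values themselves are kept and analysed, but the wording is worth correcting because AE incidence and severity are part of the primary endpoint.

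**What to change.** In Protocol 11.3.2, delete the clause that makes recording depend on the finding not being explained by disease or concomitant medication. State instead that a clinically significant vital-sign finding that is new, or has worsened, after consent goes on the AE eCRF under 12.1.2.3, with its cause entered in the causality field. This brings the section into line with 11.3.5 and Section 12.

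Align the eCRF completion guideline and tell sites of the change. The SAP needs no change on this point. The cost is one sentence in the protocol, a guideline update, and some additional AEs listed in every arm. No information on cause is lost, because the causality grade records it. The new wording would not by itself recover events already omitted.
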